9.15.4.3 Classification of Adverse Event Outcome

For each recorded AE or SAE, the Investigator or designee must make an assessment of outcome at the time of last observation. The outcome of AEs or SAEs will be documented as outlined in Table 6.

Table 6 Classifications for Adverse Event Outcomes

Classification	Definition
Fatal	The subject died.
Resolved	The AE or SAE has ended.
Resolved with sequelae	The AE or SAE has ended but changes are noted from baseline.
Unresolved	
The AE has not ended.
 
An AE outcome can only be categorized as unresolved, if the AE is
 
 ongoing at the end of the reporting period (ie, 14 days after the final Follow-up visit) and the Investigator deems that further follow-up is not medically required lost to follow-up after repeated unsuccessful attempts to contact the subject ongoing and referred to the subject's physician or a specialist

9.15.5 Reporting Procedures

Any SAE—expected or unexpected, irrespective of relationship to study treatments, including death due to any cause—experienced by a study subject will be reported to Syneos Health Safety and Pharmacovigilance by the Investigator or designee within 24 hours of learning of the event.

The contact information for the Syneos Health Safety and Pharmacovigilance is as follows:

Name	Drug Safety and Pharmacovigilance
Email	[REDACTED]
Fax	[REDACTED]

Any SAEs occurring during the trial that meet regulatory reporting criteria (ie, SUSARs) will be reported in an expedited manner to the regulatory authorities as required. Syneos Health assumes responsibility for appropriate reporting of SAEs to the sponsor in a prompt fashion. Information regarding the SAE, and all follow-up evaluations, will be transmitted to Trevi Therapeutics, Inc. by email (hard copy of documents to be scanned and attached to the email).

Contact information for the Medical Monitor in this study is as follows:

[REDACTED] MD

Medical Monitor
[name]
[name]
[name] USA

Tel.: [REDACTED]

Fax: [REDACTED]

Email: [REDACTED]

Trevi Therapeutics, Inc. is responsible to report SUSARs to Regulatory authorities (eg, FDA) and Investigator. The Investigator must report these events to their local Independent Ethics Committee (IEC) that approved the protocol per the IEC's documented requirements.

All additional follow-up evaluations for SAEs will be reported to Syneos Health Safety and Pharmacovigilance.

9.15.6 Suspected, Unexpected, Serious Adverse Drug Reactions

The Sponsor is responsible for notifying the FDA of suspected, unexpected, serious adverse drug reactions (SUSARs) observed during conduct of studies in which the Investigational Product is administered.

FDA notification of fatal or life-threatening suspected, unexpected, serious adverse drug reaction must be made as soon as possible, but no later than 7 calendar days after becoming aware of the information. FDA notification of all other suspected, unexpected, serious adverse drug reactions that are neither fatal nor life-threatening must be made as soon as possible, but no later than 15 calendar days after becoming aware of the information.

The Sponsor is responsible to comply with any other applicable regulatory requirement(s) related to the reporting of SAE to other regulatory authority(ies).

9.15.6.1 Serious Adverse Event Reporting to the Independent Ethics Committee

It is the responsibility of the sites to report as soon as possible, but no later than 7 calendar days after first knowledge by the Investigator, fatal or life-threatening suspected, unexpected, serious adverse drug reactions to the IEC responsible for the study.

It is the responsibility of the sites to report to the IEC all other suspected, unexpected, serious adverse drug reactions that are neither fatal nor life-threatening, as soon as possible, but no later than 14 calendar days after first knowledge by the Investigator.

9.16 Pregnancy

If a subject participating in the study becomes pregnant during the study, the Investigator should report the pregnancy to the Sponsor within 24 hours of being notified.

A subject becoming pregnant while on the IP will immediately be withdrawn from the study and early termination study procedures will be performed.

The subject should be followed by the Investigator until completion of the pregnancy. If the pregnancy ends for any reason before the anticipated date, the Investigator should notify the Sponsor. At the completion of the pregnancy, the Investigator will document the outcome of the pregnancy. If the outcome of the pregnancy meets the criteria for immediate classification as an SAE (ie, postpartum complication, spontaneous abortion, stillbirth, neonatal death, or congenital anomaly), the Investigator should follow the procedures for reporting an SAE.

9.17 Reportable Disease

In the case a subject has or manifested any clinical signs characteristic of a reportable disease or condition (eg, HIV, tuberculosis, SARS), it is the responsibility of the Medical Director to notify the public health department of the State of Florida within 72 hours after becoming aware of the information.

10. Study Termination

The study may be terminated by the Investigator following consultation with the Sponsor, by the Sponsor or by the regulatory authorities. Following a decision to discontinue the trial, the Investigator will immediately inform the active study subjects and the IEC responsible for this trial, stating the reasons for discontinuation of the study and, furthermore, advise them in writing of any potential risks to the health of study subjects or other persons. It is the Sponsor's responsibility to report the premature termination of the study to the regulatory authority(ies), when required by the applicable regulatory requirement(s).

11. Analytical Methodology

When applicable, samples will be transported to the bioanalytical facility in at least two separate shipments, with each set of aliquots in separate shipments. Once the bioanalytical laboratory confirms receipt of the first shipment, the second set of aliquots may be sent. The samples should be packed on sufficient dry ice to keep them frozen for at least 72 hours.

The Bioanalytical Division of Covance labs will analyze nalbuphine and its metabolite(s) (for select samples) in plasma using validated methods.

Analyst and Watson LIMS (Laboratory Information Management System) will be used at different steps of the analysis.

Samples from subjects included in the pharmacokinetic population (see Section [12.2.2](#)) and from subjects who were withdrawn from the study due to adverse events, or vomiting episodes will be analyzed.

12. Pharmacokinetic and Statistical Analyses

Pharmacokinetic analysis will be performed using Noncompartmental Analysis. Inferential statistical analyses will be performed according to FDA guidelines.

12.1 Pharmacokinetics

The following pharmacokinetic parameters will be calculated by standard non-compartmental methods for nalbuphine and metabolites (if required).

Part 1 (SAD):

- 1) AUC_{0-t} : area under the concentration-time curve from time zero to the last non-zero concentration
- 2) AUC_{0-inf} : area under the concentration-time curve from time zero to infinity (extrapolated)
- 3) C_{max} : maximum observed concentration
- 4) T_{max} : time of observed C_{max}
- 5) $T_{1/2\text{ el}}$: elimination half-life
- 6) Residual area: calculated as $100 \times (1 - AUC_{0-t} / AUC_{0-inf})$
- 7) K_{el} : elimination rate constant
- 8) Cl/F : apparent total body clearance of the drug from plasma
- 9) V_d/F : apparent volume of distribution, calculated as $Dose / (K_{el} \times AUC_{0-inf})$

Part 2 (MAD), Day 1:

- 1) AUC_{0-12} : area under the concentration-time curve from time zero to the 12-hour period
- 2) AUC_{0-24} : area under the concentration-time curve from time zero to the 24-hour period
- 3) C_{max} : maximum observed concentration
- 4) T_{max} : time of observed C_{max}

Part 2 (MAD), Days 4, 7, and 10:

- 1) AUC_{0-12} : area under the concentration-time curve from time zero to the end of the dosing period
- 2) C_{max} : maximum observed concentration
- 3) T_{max} : time of observed C_{max}

Part 2 (MAD), Day 13:

- 1) AUC_{0-12} : area under the concentration-time curve from time zero to the 12-hour period
- 2) AUC_{0-24} : area under the concentration-time curve from time zero to the 24-hour period
- 3) AUC_{0-t} : area under the concentration-time curve from time zero to the last non-zero concentration
- 4) AUC_{0-inf} : area under the concentration-time curve from time zero to infinity (extrapolated)
- 5) C_{max} : maximum observed concentration
- 6) C_{trough} : last observed concentration
- 7) T_{max} : time of observed C_{max}

- 8) Fl(%): percentage of fluctuation
- 9) Residual area: calculated as $100 \times (1 - AUC_{0-t} / AUC_{0-inf})$
- 10) $T_{1/2\text{el}}$: elimination half-life
- 11) K_{el} : elimination rate constant
- 12) Cl/F: apparent total body clearance of the drug from plasma
- 13) V_d/F : apparent volume of distribution, calculated as $\text{Dose} / (K_{el} \times AUC_{0-inf})$

Additional PK analysis may be performed. Upon the Sponsor's request, PK repeats might be performed. If re-assays are requested for PK reasons, final results will include re-assay values, while results with original values will be presented in an appendix of the report as supportive data.

12.2 Analysis Populations

12.2.1 Safety Population

The safety population is defined as all subjects who received the Investigational Product (IP).

12.2.2 Pharmacokinetic Population

The PK population will include all subjects completing one dose level of the study and for whom the PK profile can be adequately characterized. This Analysis will be conducted if warranted and reported separately.

12.3 Statistical Analyses

A Statistical Analysis Plan (SAP) will be prepared after completion of the final protocol and finalized prior to database lock.

Demographic parameters will be summarized descriptively. Treatment-emergent adverse events will be summarized descriptively by treatment for all subjects who were dosed (safety population). No inferential statistical analysis of safety data is planned.

Individual and mean plasma concentration versus time curves will be presented for both linear and semi-log scales. Descriptive statistics (arithmetic and geometric means, standard deviation [SD], coefficient of variation [CV (%)], minimum [Min], maximum [Max], and median) of the plasma concentrations versus time will be presented as well for the PK parameters according to the hepatic function groups included in the study (Control, Mild, Moderate, and Severe hepatic impairment). A graphical description of the relationship between measures of hepatic function and PK parameters will be presented. This may include the Child-Pugh classification scores (group and individual scores) or its individual components such as S-albumin, S-bilirubin, and prothrombin time expressed as INR.

For Part 1, for plasma nalbuphine and metabolite(s), for each dose level, using GLM procedures in SAS, ANOVA will be performed on untransformed K_{el} and $T_{1/2\text{el}}$ and on ln-transformed dose-normalized AUC_{0-t} , AUC_{0-inf} , and C_{max} at the alpha level of 0.05 to compare groups (Control, Mild, Moderate, and Severe). Factor incorporated in the model will include group as a fixed effect. The 90% CIs (Mild/Control, Moderate/Control, and Severe/Control) will be calculated for AUC_{0-t} , AUC_{0-inf} , and C_{max} . For these analytes, T_{max} will be analyzed non-parametrically with point

estimates and 90% CIs for the median differences of T_{max} between groups (Mild-Control, Moderate-Control, and Severe-Control).

Within each group, dose proportionality will be assessed by a visual assessment of the individual and mean nalbuphine and metabolites PK parameters.

For Part 2, for each day (as appropriate), using GLM procedures in SAS, ANOVA will be performed on untransformed K_{el} and $T_{1/2\ el}$ and on ln-transformed AUC_{0-12} , AUC_{0-24} , AUC_{0-t} , AUC_{0-inf} , C_{max} , and C_{trough} at the alpha level of 0.05 for nalbuphine and metabolite(s).

Also, for Part 2 of the study, a repeated measures analysis of variance (RMA) will be carried out on ln-transformed pre-morning and evening dose (when applicable) concentrations (Days 2, 3, 5, 6, 8, 9, 11, 12, and 13) to determine attainment of steady state.

Within each group, dose proportionality will be assessed by a visual assessment of the individual and mean nalbuphine PK parameters. A power model analysis may also be performed to evaluate the doses-exposure, if warranted.

In the event that hepatic impairment has a clinically relevant effect on nalbuphine and metabolite(s) PK, the relationship between measures of hepatic function and appropriate PK parameters (eg CL/F , AUC_{0-12} , AUC_{0-24} , AUC_{0-t} , AUC_{0-inf} , AUC_{0-t} , C_{trough} , and C_{max}) will be determined by a linear or non-linear regression.

Study results including the graphical description and the relationships between hepatic function and relevant PK parameters will be used to elaborate specific dosing recommendations if deemed clinically relevant.

For the WI-NRS variables, post-dose scores will be assessed as an increase or decrease relative to the pre-dose values. Each time point will be evaluated separately, relative to the baseline (pre-dose). Pair-wise comparisons among the group will be made if applicable.

Review of interim safety analyses will be performed between cohorts or groups. Interim PK analyses could be performed between cohorts or groups if requested or warranted.

A complete description of the statistical analyses to be performed with the safety and tolerability data, as well as PK parameters will be presented in the SAP, which will be finalized prior to database lock. Additional statistical analysis may be performed and will be described in the SAP.

13. Informed Consent

Potential subjects must provide written consent to participate after the nature, scope, and possible consequences of study have been explained in a form understandable to them.

An ICF that includes information about the study will be prepared and given to the subject. This document will contain all the elements required by the ICH E6 Guideline for GCP and any additional elements required by local regulations. The document must be in a language understandable to the subject and must specify who informed the potential subject. Where required by local law, the person who informs the potential subject must be a physician.

After reading the ICF, the potential subject must give consent in writing. The subject's consent must be confirmed at the time of consent by the personally dated signature of the subject and by the personally dated signature of the person conducting the informed consent discussions.

A copy of the signed ICFs must be given to the subject. The original signed ICFs will be retained by the Investigator.

The Investigator will not undertake any measures specifically required only for the clinical study until valid consent has been obtained.

14. Regulatory Considerations and Quality Assurance

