5.2.1 Rationale for a Single- and Multiple-Escalating Dose Design

This study will include both a single-ascending-dose (SAD) portion and a multiple-ascending dose (MAD) portion. The PK, safety, and tolerability of single ascending doses (SAD) of NAL ER (4 dose levels) will be evaluated in subjects with mild and moderate hepatic impairment. Severe hepatic subjects will be evaluated at a single dose of 27 mg.

The purpose of the SAD will be to assess the safety and PK parameters of the given dose levels in hepatic impaired subjects relative to a selected healthy subject control population as part of the overall NAL ER development program. The SAD will also allow a better understanding of the safety, tolerability and expected steady state PK characteristics in mild and moderate hepatic impairment prior to undertaking safety and itch suppression efficacy studies in this patient population.

In the MAD portion of this study, PK assessment will be carried out at steady state at each respective dose level at steady state during the titration over 13 days up to the highest planned therapeutic dose of 162 mg. It is well documented, in clinical practice and the opiate literature, that gradually increasing the dose of drug with a structured titration can reduce the frequency and severity of the expected AEs associated with initiation of therapy. The NAL ER clinical program utilizes this type of structured titration strategy, starting with once per day dosing at the 27 mg dose of NAL ER, and increasing the dose in a stepwise manner over the next 13 days to the target investigational dose of 162 mg twice daily. Pharmacokinetic steady state is reached after 2 to 3 days of 162 mg twice daily.

Once the Part 1 SAD portion of the study is completed, if in the judgement of the Safety Committee the PK data demonstrates dose linearity across the dose range in both the mild and moderate hepatic impairment subjects (Group 1 and Group 2 subjects), such that PK modeling can be predictive of steady state dosing levels, a decision may be made to end the study without conducting Part 2 of the study.

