#### **4. Changes from the Protocol**

No changes in planned analyses were done compared to the protocol.

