## 8.6 Steady-State Attainment

For Part 2 of the study, a repeated measures analysis of variance (RMA) will be carried out on ln-transformed pre-morning and evening dose (when applicable) concentrations (Days 2, 3, 5, 6, 8, 9, 11, 12, and 13) to determine attainment of steady state.

Repeated measures analysis of the last three pre-dose concentrations (Ln transformed) will be statistically analyzed using General Linear Model (PROC GLM) of SAS® version 9.4 software.

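### The steady-state test in Part 2 is written on two incompatible sets of troughs: one pools a 6-fold dose titration and cannot show steady state, and the other, taken over the study, tests only 162 mg

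*Protocol*

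**What the plan says.** Protocol 12.3 says a repeated-measures ANOVA for Part 2 will use the ln-transformed troughs taken before the morning and evening doses, that is, "concentrations (Days 2, 3, 5, 6, 8, 9, 11, 12, and 13) to determine attainment of steady state". SAP 8.6 opens with the same sentence: "For Part 2 of the study, a repeated measures analysis of variance (RMA) will be carried out on ln-transformed pre-morning and evening dose" and the same list of days.

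The next paragraph of SAP 8.6 describes the data differently: "Repeated measures analysis of the last three pre-dose concentrations (Ln transformed) will be statistically analyzed using General Linear Model". It does not say whether the last three are taken over the whole study, within each dose level, or from mornings only.

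Neither document gives this test a null hypothesis, an alpha, model factors or contrasts. Neither mentions dose normalisation for it, although Protocol 12.3 does specify dose normalisation for the Part 1 ANOVA. Protocol 12.3 leaves the detail to the SAP ("A complete description of the statistical analyses to be performed with the safety and tolerability data, as well as PK parameters will be presented in" that document). SAP Section 4 states: "No changes in planned analyses were done compared to the protocol".

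Protocol 5.2.1 gives the purpose: "PK assessment will be carried out at steady state at each respective dose level at steady state during the titration". In the titration table (Protocol 9.4, SAP Table 3-2), the pre-dose samples on the listed days follow 27 mg on Days 2-3, 54 mg on Days 5-6, 108 mg on Days 8-9 and 162 mg on Days 11-13.

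**The concern.** A repeated-measures ANOVA of troughs over time asks whether the mean trough is the same at every time point. That is a sensible steady-state question only while the dose is constant. Across the listed days it is not, so equality is false by design, whatever the state of accumulation. Taking logs turns the 6-fold rise into an additive shift but does not remove it.

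The second SAP paragraph avoids this problem if it means the last three samples of the study, but the test then covers only the top dose. The Day 4, 7 and 10 profiles supply the exposure at 27, 54 and 108 mg and feed the Part 2 dose-proportionality summaries in SAP 8.8.2. Under that reading their steady-state status is not tested. Whether hepatically impaired subjects reach steady state in two to three days is a real question, because the supporting data come from healthy subjects. With two data sets on the page, the choice between them could also be made after the data are seen.

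**Working it through.** **Samples in the pooled test.** Eight of the listed days have a morning and an evening trough, and Day 13 has a morning trough only: 8 × 2 + 1 = 17. By the dose last taken, these are 4 at 27 mg, 4 at 54 mg, 4 at 108 mg and 5 at 162 mg.

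**The plan's own figure.** The documents give no error rate for this test. The one steady-state figure that can be checked is the accumulation ratio of 1.61 (Protocol Table 2, healthy subjects):
- From the AUCs: 50.88 / 31.53 = 1.614.
- From the Day 13 half-life of 8.58 h and a 12 h interval: q = exp(−ln 2 × 12 / 8.58) = 0.3793, and 1 / (1 − q) = 1.611.

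The figure is reproduced, so mono-exponential superposition is used below.

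**Size of the dose effect.** The dose ratio is 162 / 27 = 6, and ln 6 = 1.79. With every trough exactly at steady state for its dose, the ln means relative to 27 mg are 0, 0.693, 1.386 and 1.792, with 4, 4, 4 and 5 samples. Their mean is 17.277 / 17 = 1.016. The sum of squared deviations is 4 × 1.033 + 4 × 0.104 + 4 × 0.137 + 5 × 0.601 ≈ 8.10. For n = 6 and within-subject CV 100%, the ln-scale variance is ln(1 + 1²) = 0.693, so the noncentrality is 6 × 8.10 / 0.693 ≈ 70. Smaller CVs or larger n make it larger still.

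**Simulated rejection rates** (one-way within-subject F test). Assumptions: alpha 0.05; within-subject CV 15% to 50%, and up to 100% for the pooled test; half-life 8.58 h, or 17 h as an assumed value for impairment. n runs from 6 to 16, since Part 2 enrols up to 8 per group.

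| Data set | Condition | Rejection |
|---|---|---|
| All 17 samples | Exact steady state at every dose | at least 99.98% |
| All 17, dose-normalised | 8.58 h or 17 h | at least 99% |
| Last three of study (Day 12 AM, Day 12 PM, Day 13 AM) | Exact steady state | 4.5% to 5.7% |
| Same three | 8.58 h | 4.7% to 5.8% |
| Same three | 17 h | 5.4% to 13.7% |
| Last three mornings (Days 11, 12, 13) | 8.58 h | 6% to 66% |

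**Why dose normalisation is not enough.** Let f be the trough as a fraction of its steady-state value for the dose last taken. At each 12 h step, f(next) = q × f × (previous dose / latest dose) + (1 − q). With q = 0.3793:
- Day 2 AM (one dose, 24 h earlier): q(1 − q) = 0.235
- Day 2 PM: 0.3793 × 0.235 + 0.6207 = 0.710
- Day 3 AM 0.890; Day 3 PM 0.958; Day 4 AM 0.984; Day 4 at 12 h 0.994
- Day 5 AM (first 54 mg dose taken): 0.3793 × 0.994 × 27/54 + 0.6207 = 0.809
- Day 11 AM (first 162 mg dose taken): 0.3793 × 0.9985 × 108/162 + 0.6207 = 0.873, where 0.9985 is the Day 10 12 h value from the same recursion

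Early samples at each level are truly below steady state, so normalising all 17 and testing for a time effect still rejects. The listed days also omit Days 4, 7 and 10, whose pre-morning and 12 h samples are the last troughs at 27, 54 and 108 mg.

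**The case against.** The strongest reply is that the SAP is the operative document and its second paragraph narrows the test to three samples. If those are the last three of the study, all follow 162 mg and the error rate at steady state is about 5%. This stands. A reader might infer that the trial's steady-state test is certain to reject because of titration; the documents support that only for the pooled-day sentence. But the sentence is still in both documents, and the SAP declares no change from the protocol.

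A second reply is that the listed days form dose blocks, so the last three could mean the last three in each block. That is sensible, but it is not stated. On the listed days alone, the 27 mg block would be Day 2 PM, Day 3 AM and Day 3 PM. Day 2 PM is at about 71% of steady state, and that test rejects in 28% to 39% of runs at CV 30% with 6 to 8 subjects (half-life 8.58 h).

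Third, no null or decision rule is written, so reading the analysis as one overall F test is an assumption. The 100% case, with all 17 samples at steady state, is also one that this titration cannot produce. Both points are fair. The calculation shows only that dose alone is enough to cause rejection.

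Fourth, Part 2 is optional, and no dose decision or exclusion is tied to this test. That limits the stakes.

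The three samples at 162 mg also mix one evening trough with two morning ones. A reader might infer bias from a day-night difference, but the documents report none, so any figure would rest on assumption.

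**Conclusion.** The point holds as a defect of specification. One test has two data sets. The pooled-day version in Protocol 12.3 and the first paragraph of SAP 8.6 cannot show steady state: it rejects in at least 99.98% of runs from dose alone. The last-three version, taken over the study, is sound at 162 mg (about 5% rejection at steady state) but leaves three of the four dose levels untested, contrary to the aim in Protocol 5.2.1.

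It does not follow that the Day 4, 7 and 10 profiles are off steady state. At a half-life of 8.58 h the Day 4 AM trough is about 98% of steady state; at an assumed 17 h it is about 89%. What is missing is a test that could tell these apart at each level.

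The result rests on an assumed overall F test at alpha 0.05 and assumed within-subject CVs, since Protocol 5.1.1.2 calls within-subject variability lower without giving a value. The contrast between the pooled and constant-dose tests holds over the whole range tried. Non-rejection with so few subjects is weak evidence: at 17 h, Day 12 AM is at 92% of steady state, yet the test on the last three samples rejects in only 5.4% to 13.7% of runs.

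**What to change.** In Protocol 12.3 and SAP 8.6:

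- Delete the sentence that pools the listed days.
- Run the repeated-measures analysis separately within each dose level, on the last three pre-dose samples at that level. Include the Day 4, 7 and 10 pre-morning samples and the 12 h samples taken before the evening dose. For example, use Day 3 PM, Day 4 AM and Day 4 at 12 h for 27 mg, and Day 12 AM, Day 12 PM and Day 13 AM for 162 mg.
- State the alpha and the model factors, and report a conclusion for each dose level.
- Do not substitute dose normalisation across all days.
- A sensitivity check for morning versus evening troughs is optional.

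All the samples are already scheduled. The cost is wording in two sections and a small amount of extra analysis.
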